9.4.2 ANALYSIS OF THE PRIMARY EFFICACY ENDPOINT(S)

Aim 1.1.

Using the analytical software of APDM, the SWAY and TUG algorithms included in the SAW test will calculate asymmetry and variability for: postural sway (RMS AP & ML planes), cadence (CN), gait cycle duration, gait speed (SN), swing, double support, elevation at midswing, foot strike angle, toe off angle, stance, step duration, stride length (LN), arm swing velocity, arm range of motion, turn angle, turn duration, and turn velocity. All data will be tested for normality with Shapiro-Wilk test. Linear mixed models with repeated measures (LMMRM) will be used to compare high and low frequency over all contact pairs in the levodopa-OFF state. Parameter estimation will be based on restricted maximum likelihood and the form of the covariance matrix will be chosen based on Akaike's Information Criteria and Schwarz' Bayesian Criterion. The Holm-Bonferroni method will be used to adjust for multiple comparisons for the 20 outcome measures.

Aim 1.2. To investigate levodopa's effects on the gait domains, we will include the data for levodopa-ON and add a binary variable for levodopa (on or off) to the LMMRM from Aim1.1.

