Aim 2.1. We will utilize the raw data collected during Phase II to develop regression models, under both ON and OFF medication states for all contact pairs. The top panel in Figure 2 presents the overview of Aim 2.1; the goal of this sub-Aim is to predict the gait parameters for patients on low frequency by using the gait sensor measurements obtained on high frequency. Additional independent variables/regressors include general patient/disease characteristics such as age, gender, and disease duration. We will also build models under both ON and OFF medications. To develop the regression models, we use non-linear regression analysis based on random forest (RF) classifier. RF is based on an ensemble of decision trees, referred to as a 'forest,' where predictions for any new observation are obtained from averaging the predictions of individual trees (56). Generally, RF models are not prone to overfitting and are robust against noisy or high-dimensional datasets (57). In addition, they are generally interpretable, allowing for further examination of results and easier subject subtyping with respect to symptomology. However, to assure that the RF based models are the best performing models, we also develop models based on some of the other machine learning techniques, such as neural networks (56), and use them as benchmarks. If needed, to improve model performance we will perform model building in RF models to identify and include the most important parameters (38). We will use techniques such as cross-validation (e.g., leave-one-out) and bootstrapping to examine the generalizability of the models and acquire confidence intervals for the predicted values. Lastly, we will compare the best performing models obtained for both ON and OFF medications and their most important contributing parameters to further investigate the interaction of medications and stimulation frequency.

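### Aim 2.1 names only neural networks as a benchmark for its random forest, which is unlikely to reveal shrinkage that can look like a 60 Hz gain in the slowest walkers

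*Combined protocol and SAP*

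**What the plan says.** Under Aim 2.1 in section 9.4.2 the goal is to "predict the gait parameters for patients on low frequency by using the gait sensor measurements obtained on high frequency". Patient characteristics are added as predictors: "Additional independent variables/regressors include general patient/disease characteristics such as age, gender, and disease duration". The learner is stated as "To develop the regression models, we use non-linear regression analysis based on random forest (RF) classifier", and the section explains that "predictions for any new observation are obtained from averaging the predictions of individual trees".

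To confirm that the forest performs best, "we also develop models based on some of the other machine learning techniques, such as neural networks (56), and use them as benchmarks". The objectives table in section 3 repeats this. For validation, "We will use techniques such as cross-validation (e.g., leave-one-out) and bootstrapping to examine the generalizability of the models"; the text does not say whether a whole patient or a single trial is left out.

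No section commits Aim 2 to a linear model, a no-change rule (60 Hz value equals the patient's own HFS value) or a calibration check. Section 9.1 asks that accuracy be statistically significant but gives no accuracy measure and no comparator. The aims in sections 1.1 and 2.1 give the purpose as predicting how gait responds to 60 Hz without having to test it.

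**The concern.** The best predictor of a patient's gait at 60 Hz is likely to be the same parameter, in the same patient, at high frequency. If that relation is close to a straight line with slope near 1, a forest suits it poorly. Each prediction is an average of training outcomes, so it cannot go beyond them, and in a small sample it flattens both ends of the range. Slow walkers are then predicted too fast and fast walkers too slow.

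Read against the patient's measured HFS gait, that error looks like a 60 Hz benefit in the slowest walkers. Section 5.1 requires a gait disorder for entry, so these patients matter most. A model can meet the section 9.1 hypothesis and still carry the error, because the wide spread between patients gives a high R² by itself. A neural network fitted to so few patients is a weak yardstick. Section 9.4.2 remarks that forests resist overfitting, but that does not address shrinkage toward the mean.

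**Working it through.** **1. The plan's own figures.** Section 9.2: 15.79 × 0.03 / 0.14² = 24.17, taken as 24. Then 24 × 1.2 = 28.8, taken as 29, and the final figure is 30 (also 24 / 0.8). This compares walking speed in healthy people and PD patients and does not size Aim 2. It supplies the sample size (24 to 30) and a yardstick (0.14 m/s).

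**2. Inputs from the documents.** PD stride velocity is 0.99 (SD 0.18) without freezing and 0.86 (SD 0.21) with it (section 9.2). An equal mix has mean 0.925 and SD √[(0.18² + 0.21²)/2 + 0.065²] = √(0.03825 + 0.00423) = 0.206 m/s. There are four contact pairs at two frequencies, so eight trials per medication state (section 4.1). On the number of gait measures: "The Holm-Bonferroni method will be used to adjust for multiple comparisons for the 20 outcome measures".

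**3. Assumed inputs, not in the documents.** Contact SD 0.04 m/s; trial noise SD 0 to 0.10 m/s; other gait features correlated 0 to 0.9 with speed; a linear relation between HFS and 60 Hz speed. Only speed was simulated.

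**4. Nobody changes.** 60 Hz speed was set equal to HFS speed for every patient, with noise SD 0 to 0.08, models pooled over contact pairs and whole patients left out. The slope of the forest's prediction on HFS speed was 0.58 to 0.88 at n = 24 and 0.60 to 0.92 at n = 30, where no change is 1. Treating the forest as a line through the mean, a patient one SD slow has a predicted gain of (1 − slope) × 0.206, which is 0.016 m/s at slope 0.92 and 0.087 at slope 0.58. The simulated slowest quarter had predicted gains of 0.014 to 0.093 m/s.

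Part of this is ordinary regression to the mean. At n = 30 and noise SD 0.08, one forest setting predicted a gain of 0.066, of which 0.013 was the actual difference in measured speed and 0.053 was forest bias.

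**5. Patients differ but the mean change is zero.** Individual differences had SD 0.05 to 0.10. Across separately coded simulations the forest over-predicted the slowest tenth by 0.04 to 0.13 m/s, that is 0.04/0.14 = 29% to 0.13/0.14 = 93% of the section 9.2 difference. It under-predicted the fastest tenth by 0.06 to 0.12 in the runs that reported it. A one-variable linear fit had slow-end bias between −0.02 and +0.02.

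**6. Would the named benchmark reveal it?** From the step 4 setting (MAE is mean absolute error, m/s):

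| n, noise SD | No change: MAE, R² | Forest: MAE, R² | Neural network: MAE, R² |
|---|---|---|---|
| 24, 0.05 | 0.058, 0.88 | 0.073–0.077, 0.77–0.79 | 0.101, 0.63 |
| 30, 0.05 | 0.055, 0.89 | 0.064–0.069, 0.81–0.84 | 0.095, 0.66 |
| 30, 0.08 | 0.091, 0.70 | 0.093–0.094, 0.69 | 0.147, 0.21 |

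The neural network was never more accurate than the forest where both were run. At noise SD 0.05 the forest wins the planned comparison yet has 26–33% (n = 24) or 16–25% (n = 30) more error than assuming no change.

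**7. Sensitivity.**
- Root mean squared error against the linear fit: the forest was 13–50% worse at noise SD 0.03 to 0.05 across two sets of runs, 0–6% worse at 0.08, and between slightly better and about 9% worse at 0.10.
- One model per contact pair (noise SD 0.05, setting of step 4): slope 0.57–0.72, slowest-quarter gain 0.07–0.12.
- Forest restricted to its top three predictors: slow-end bias fell from 0.066–0.094 to 0.051.
- Single trials left out instead of patients (n = 24): slope 0.85–0.90, gain 0.02–0.04. The patient's other trials stay in training and hide most of the shrinkage.

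Replicates were few (8 per main cell in step 4, 15 for per-contact models, 3 for single-trial deletion), so the figures are approximate.

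**The case against.** The linear link is assumed; the documents do not state it. Section 9.1 expects gait parameters to be affected differently by the two frequencies, and an additive simulated truth favours the linear comparator. When response was made to depend on a speed threshold (slow walkers gain 0.20, others lose 0.10), forest and linear errors were within about 4% of each other, and the linear model under-predicted the slow end by 0.01 to 0.04. This stands. It is a reason to include a linear comparator, not to replace the forest.

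The benchmark wording is open-ended, cross-validation is planned and variable selection is allowed. Also true: a linear model could be added, but nothing commits the team to one, and selection reduced the bias without removing it.

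Section 9.4.2 does not say that predicted 60 Hz gait will be set against measured HFS gait to choose a frequency. Choosing the frequency belongs to Aim 2.2. The stated purpose of Aim 2.1, response to 60 Hz without testing it, still invites that reading.

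A reader might infer that the forest is simply less accurate than a one-variable regression. That depends on trial noise, which the documents do not give; at SD 0.10 a forest matched or slightly beat the linear fit in some runs by drawing on correlated gait features.

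**Conclusion.** The point holds as a gap in benchmarks and calibration for Aim 2.1. Under a roughly linear link and no mean frequency effect, the forest over-predicts the slowest tenth by about 0.04 to 0.13 m/s, a sizeable share of 0.14 m/s. The direction was the same in every no-mean-effect setting run, while the size depends on noise, tuning and variable selection. The accuracy penalty against a linear fit is clear at trial noise SD 0.03 to 0.05 m/s and largely disappears at 0.08 to 0.10.

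Three stronger readings are not supported.
- That slow walkers will be predicted to gain when nobody does: this describes only the zero-effect simulation, and there it is a group tendency, with 45–97% of the slowest quarter predicted to gain.
- That Aim 2.2 has the same fault: it predicts both frequencies from baseline, so shrinkage may partly cancel, and this was not tested.
- That a linear model must become the base model: this is a preference, and the documents give no ground for it.

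**What to change.** In section 9.4.2, Aim 2.1:

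- Require two benchmarks beside the neural network: (a) no change, with the 60 Hz value set to the patient's own HFS value; (b) a linear (mixed) regression of each 60 Hz parameter on the same parameter's HFS value.
- Compare all models with whole patients left out.
- Report the calibration slope of observed on predicted values, and the slope of predicted change on HFS value. Set the second beside the slope for observed change, since noise alone tilts it.
- Claim predictive value for the forest only if its left-out-patient error is lower than that of both benchmarks.

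A forest fitted to the residual of the linear model can be an optional candidate. Error by tenth should not be required, because a tenth of 24 to 30 patients is only 2 to 3 people.

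The cost is a few sentences and some extra fits on the same data, with no new patients or visits. The downside for the team is that the forest may not prove to be the best model.

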1 PROTOCOL SUMMARY

1.1 SYNOPSIS

Title: Computational Modeling of 60 Hz Subthalamic Nucleus Deep Brain Stimulation for Gait Disorder in Parkinson's disease

Study Description: The goal of this research is to further our understanding and application of deep brain stimulation in Parkinson's patients with gait disorder.

We will assess the degree to which stimulation parameters affect gait parameters. We will test the hypothesis that the addition of levodopa in combination with stimulation produces a synergistic improvement in certain gait domains. In addition, we test the hypothesis that a subject's gait on stimulation can be predicted with statistically significant accuracy using gait measurements on high frequency stimulation. Finally, we will test the hypothesis that the best stimulation frequency, which yields improvement among various gait parameters, can be predicted using objective sensor data collected at baseline

Objectives:

Aim 1: To determine the impact of 60Hz subthalamic deep brain stimulation on gait kinematics using wearable sensors

- Aim 1.1: To determine whether 60Hz STN-DBS elicits a differential response in gait kinematics compared to high frequency
- Aim 1.2: To determine the influence of 60Hz STN-DBS and levodopa on gait kinematics

Aim 2: To develop machine learning models to predict optimal subthalamic deep brain stimulation frequency based on wearable sensor profiles of baseline Parkinson's motor symptoms

- Aim 2.1: To develop machine learning models to predict gait response to 60Hz stimulation without additional testing
- Aim 2.2: To develop machine learning models to predict best stimulation frequency (60Hz vs. high frequency).

Endpoints:

Primary Endpoints:

Gait parameters:

- Postural sway – root mean square (RMS) sway in antero-posterior (AP) and medio-lateral (ML) planes;
- Gait – cycle duration (seconds), speed (m/s), stance (%), swing (%), heel strike angle (degrees), toe off angle (degrees), stride length (cm), cadence (steps/min), step duration (seconds), elevation at midswing (cm) (foot clearance), double support (%), arm swing velocity (deg/s), and range of motion (degrees);

- Circumduction – turn angle (degrees), turn duration (seconds), and turn velocity (deg/s).

Machine learning models to: 1) predict gait kinematics on 60Hz STN-DBS; 2) predict best stimulation frequency using wearable sensor data collected at baseline.

Secondary Endpoints:

Tremor (rest, kinetic, postural)

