- **Aim 1: To determine the impact of 60Hz subthalamic deep brain stimulation on gait kinematics using wearable sensors**
 - Aim 1.1: To determine whether 60Hz STN-DBS elicits a differential response in gait kinematics compared to high frequency
 - Aim 1.2: To determine the influence of 60Hz STN-DBS and levodopa on gait kinematics
- **Aim 2: To develop machine learning models to predict optimal subthalamic deep brain stimulation frequency based on wearable sensor profiles of baseline Parkinson's motor symptoms**
 - Aim 2.1: To develop machine learning models to predict gait response to 60Hz stimulation without additional testing
 - Aim 2.2: To develop machine learning models to predict best stimulation frequency (60Hz vs. high frequency).

This study will set the stage for developing a randomized trial that would assess a new paradigm for selecting DBS patients for 60Hz stimulation prior to surgery, conducting initial programming and other elaborate programming approaches under this stimulation mode, and achieving programming optimization using sensors, through a data-driven approach. In addition, the results may indicate that certain PD phenotypic subtypes are most suitable for 60Hz DBS.

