9 STATISTICAL CONSIDERATIONS

9.1 STATISTICAL HYPOTHESES

Aim 1. Our preliminary study established that gait and rest tremor are important factors to determine whether patients benefit from 60Hz stimulation or high frequency stimulation (38). However, the degree to which stimulation parameters affect gait parameters is not well established. In Aim 1, we will test the *hypothesis* that certain gait parameters are differentially affected between 60Hz and high frequency STN-DBS at various electrode contact configurations. In addition, in our preliminary analysis, we observed a modest reduction in dopaminergic medications in patients on 60Hz stimulation (12). Hence, we will also test the *hypothesis* that for some patients, the addition of levodopa in combination with 60Hz stimulation produces a synergistic improvement in certain gait domains.

Aim 2. Our preliminary data suggested that there is a link between the patient's baseline motor symptomatology measured by the MDS-UPDRS III ratings and the best stimulation frequency (60 Hz or HFS) chosen for the patient based on intensive clinical evaluations, which remained unchanged for an average of 12 months. In Aim 2, we test the *hypothesis* that a subject's gait kinematics on 60Hz stimulation can be predicted with statistically significant accuracy using gait measurements on high frequency stimulation. In addition, we will test the *hypothesis* that the best stimulation frequency (60Hz or HFS stimulation), which yields improvement among various gait parameters, can be predicted using objective sensor data collected at baseline. We define baseline motor performance as the severity of motor symptoms in the levodopa OFF and ON state without stimulation. In the remainder of this proposal, for simplicity we refer to 60 Hz stimulation and high frequency stimulation (130-180Hz) as low frequency (LFS) and high frequency (HFS), respectively.

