Aim 2.2. Similar to Aim 2.1, in this sub-Aim we conduct regression analysis to predict gait parameters. However, in this sub-Aim, gait parameters are predicted on low and high frequency in the context of ON and OFF medication conditions using baseline bradykinesia, tremor, and gait sensor measurements, plus MDS-UPDRS III rigidity and axial sub scores. Patient and disease characteristics will be used as regressors. Again, models will be based on RF classifier, where other modeling techniques, such as neural networks, will be used as benchmarks. The best performing parameters identified in Aim 2.1 will be used to guide the model building in this sub-Aim. Also, aforementioned performance enhancing techniques will be used, if possible, and confidence intervals will be generated using bootstrapping. These models will be able to predict the best stimulation frequency and contact pairs for the patient immediately after baseline evaluations and provide a confidence level. Similar to Aim 2.1, we will

develop these models with and without accounting for PD medications to further quantify their impact and provide additional options for patients.

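### Aim 2.1 has no stated error metric, null or HFS-value reference, so predicting the 60 Hz gait level with significant accuracy would not show that the model adds to the HFS measurement already in hand

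*Combined protocol and SAP*

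**What the plan says.** The synopsis (1.1) lists the Aim 2 models among the primary endpoints; the first is to "predict gait kinematics on 60Hz STN-DBS". Section 2.1 words Aim 2.1 as "To develop machine learning models to predict gait response to 60Hz stimulation without additional testing".

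The Aim 2 hypothesis in 9.1 is that gait kinematics on 60 Hz "can be predicted with statistically significant accuracy using gait measurements on high frequency stimulation". The analysis goal in 9.4.2 is to "predict the gait parameters for patients on low frequency by using the gait sensor measurements obtained on high frequency", with age, gender and disease duration as further regressors. The main learner is a random forest.

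On comparators, 9.4.2 says "we also develop models based on some of the other machine learning techniques, such as neural networks (56), and use them as benchmarks". On validation it says "We will use techniques such as cross-validation (e.g., leave-one-out) and bootstrapping to examine the generalizability of the models", and also that intervals will be obtained for predicted values. For the next step, Aim 2.2, it says "The best performing parameters identified in Aim 2.1 will be used to guide the model building in this sub-Aim".

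Neither 9.1 nor 9.4 states an error measure, a null hypothesis, a test or a threshold for the accuracy claim. Neither names a reference prediction built from the patient's own HFS value. Section 9.4.2 points to the top panel of Figure 2 for an overview of Aim 2.1, and that figure is missing from this copy.

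**The concern.** The predictor and the target are the same gait parameter in the same patient at two stimulation settings. Patients differ in stable ways that have nothing to do with frequency. Under the usual nulls (zero correlation between predicted and observed values, or prediction by the group mean), those differences alone can produce significant accuracy.

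A report of success would then leave two questions open: whether the model improves on the HFS value that was measured anyway, and whether the change from HFS to 60 Hz can be predicted. Comparing a forest with a neural network answers neither, because both can exploit the same stable differences. Aim 1.1 does not fill the gap either: it tests the difference between frequencies, not whether an individual's change can be predicted.

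Aim 2.1 is part of a primary endpoint, and its best parameters are carried into Aim 2.2. A reader could not tell whether they mark a frequency-related change or only how well the patient walks in general.

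**Working it through.** **The plan's own figure.** The only sample-size calculation (9.2) is 15.79 × 0.03 / 0.14² = 24.2, taken as 24. Allowing for 20% attrition, 24 / 0.8 = 30. It reproduces, but it rests on a walking-speed difference between healthy people and people with Parkinson's disease. It says nothing about prediction accuracy; 24 and 30 are used here only as the number of patients.

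**Inputs.** The documents give no correlation between HFS and 60 Hz gait, so the stable between-patient share of variance (ICC) is assumed at 0.5, 0.7 and 0.9.

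**Model with no frequency effect.** HFS = b + e1 and 60 Hz = b + e2, with var(b) = ICC, var(e1) = var(e2) = 1 − ICC, and independent errors. Then:

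- Correlation of HFS with 60 Hz gait = ICC, so the large-sample R² for the level is ICC² = 0.25 / 0.49 / 0.81.
- Error variance of the straight line on HFS = 1 − ICC² = 0.75 / 0.51 / 0.19.
- Error variance if the HFS value itself is carried over = 2(1 − ICC) = 1.00 / 0.60 / 0.20.

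At ICC 0.9 the line (0.19) and the untouched HFS value (0.20) are almost equal. A high R² for the level therefore coexists with nothing learned about change.

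**Simulation of the level.** Straight line on HFS, one row per patient, one patient left out at a time, no frequency effect. Results for ICC 0.5 / 0.7 / 0.9:

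| Criterion | 24 patients | 30 patients |
|---|---|---|
| Positive correlation, p<0.05 | about 44% / 91% / 100% | about 58% / 97% / 100% |
| Same, at 0.05/20 = 0.0025 | 13% / 64% / 99.9% | 22% / 82% / 100% |
| Lower error than the mean, paired test, p<0.05 | about 8% / 42% / 96% | about 12% / 59% / 99% |

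Mean out-of-sample R² at 24 patients was 0.19 / 0.44 / 0.79. The second row applies the strictest step of a Holm correction over 20 outcomes, as in Aim 1.1. Adjusting for multiplicity does not remove the problem.

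**Why the reference should be a line on HFS.** With no frequency effect, the change from HFS to 60 Hz still correlates with the HFS value through regression to the mean. The size of that correlation is √((1 − ICC)/2) = 0.50 / 0.39 / 0.22. A model can therefore beat the raw HFS value for this reason alone. A fitted line on HFS already absorbs it.

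**What beating that line would mean.** Take 24 patients with 4 contact pairs each, no frequency effect, and further gait parameters whose patient-level correlation with the target is 0.9 (assumed). The 95% patient-level bootstrap interval for the error reduction excluded zero in about 17–25% of runs with one extra parameter and 19–43% with three. These runs were few enough that repeats move the figures by several points. The extra parameters sharpen the estimate of the patient's stable level; they carry no information about frequency. With one extra parameter and correlation 0 to 0.5, such passes were 0–1%.

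**The case against.** **The target may be deliberate.** A reader might infer that the plan promises one quantity (response) and models another (level), so that the target is wrong. The documents do not support this. The fourth question in 2.1 speaks of response at both high frequency and 60 Hz, and response at high frequency cannot be the difference between the two settings. The aim of avoiding additional testing also fits predicting the level. Endpoint, hypothesis and analysis goal all agree on the level. Since HFS gait is a predictor, predicted change is simply predicted 60 Hz gait minus observed HFS gait. This objection stands in full; what remains is the undefined success criterion.

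**Presurgical selection.** A reader might infer that a hollow Aim 2.1 would directly mislead the planned selection of patients before surgery. It would not: Aim 2.1 needs gait measured on HFS, which preoperative patients do not have. Selection rests on Aim 2.2, which uses unstimulated baseline data and predicts gait at both frequencies. The link is only that Aim 2.1 guides model building there.

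**The illustration is not the planned analysis.** True. The plan uses a forest with many features, four contact pairs and two medication states, and the ICCs are assumed. Against the mean at ICC 0.5 the figure is only 8–12%. The simulation shows the mechanism and does not forecast the result.

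**The text may be incomplete here.** Figure 2 could name a metric or a reference, and the benchmark list is open. The absence is therefore one of the available text, and nothing in that text requires an HFS reference.

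**Conclusion.** The point holds as a gap in the success criterion for a primary endpoint. Followed as written, Aim 2.1 could be reported as a success when the model adds nothing to the HFS value. In the illustration a no-effect trial of 24 patients meets a correlation criterion in about 44% / 91% / 100% of runs and beats the mean in about 8% / 42% / 96%, for ICC 0.5 / 0.7 / 0.9. This rests on the assumed ICC, independent errors, a straight line, one row per patient, and a null of zero correlation or of prediction by the mean.

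The level hypothesis would be true in such a trial, so this is not a false positive for the hypothesis in 9.1. It would show neither added value over HFS nor a predictable change.

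Two stronger inferences should be avoided. Beating a line on HFS does not by itself establish that response to 60 Hz is predicted, as the 17–25% and 19–43% figures show. Nor do the documents show that validation mixes rows from one patient, or that parameter selection sits outside the folds. They do not state either way, so these are matters for a safeguard.

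**What to change.** In 9.4.2, Aim 2.1:

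1. Name one out-of-sample error metric for each gait parameter, for example RMSE.
2. Add as a reference benchmark a straight line on the patient's HFS value at the same contact pair and medication state, fitted in the training folds only.
3. Leave out and resample whole patients.
4. Report the error reduction over that reference with a patient-level bootstrap interval.
5. Fix the wording of the claim in advance. If the interval includes zero, claim only that the 60 Hz level is predictable, and do not read this as absence of response. If it excludes zero, claim only that the model improves on the HFS value, and state that this is necessary but not sufficient for predicting response.

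Fitting the model to the change from HFS to 60 Hz is optional. It may help power. In small illustrative runs (41–50 per setting, 24 patients × 4 pairs, ICC 0.7 or 0.9, assumed patient-specific response SD of 0.5 or 0.8), a forest fitted to the level showed an increment in 0–4% of runs and one fitted to the change in 10–98%.

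As safeguards rather than corrections of a shown error, feature selection, learner choice and any Aim 2.1 guidance could be kept inside the training folds. Aim 2.2 could be given simple references: the training-set mean for predicted gait, and the training-set majority frequency for the choice of frequency.

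The cost is wording and computing; no visits or measurements are added. Reported accuracy will look less favourable, and power to show an increment is limited with 24 to 30 patients.
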